We use conservative estimates of a 3.3-point difference with a standard deviation of 6 points. Calculations show that a sample size of 53 subjects per group (total 106) would provide 80% power at a 5% level of significance (two-sided) to detect the difference between treatment and sham groups.

Given our preliminary results, together with other companies clinically relevant data, we hypothesize that our statistical assumptions are aligned with competitive treatments for MDD.

The company anticipates that after randomization, but before the endpoint can be observed, up to 15% of the subjects will drop out from the study irrespective of study arm and success of treatment; thus, an adjustment for this drop-out rate is made and a sample size of 124 is required at the point of randomization.

We shall randomize an additional up to 36 subjects (30+15% dropout) in the age range 18-21 to assess efficacy in this age range as well.

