6. RANDOMIZATION AND BLINDING

Up to the date of the finalization of this SAP the treatment code was not revealed. Subjects will be prospectively randomized into the clinical study. Randomization will occur only after the subject provides informed consent, completes all required screening and baseline procedures, and satisfies the study eligibility criteria. Eligible subjects will be randomly allocated (with a 1:1 ratio) to one of the following 2 treatment groups based on a randomization scheme using the permuted block method stratified by center:

- Active stimulation.
- Sham stimulation.

The Relivion®DP Active and Sham devices will look the same and will be provided in the same packaging bearing the same labeling. Hence, both subjects and study personnel will remain blinded to the assigned treatment group. Furthermore, the sponsor, investigator, MDD assessor and device trainer are all blinded to the treatment assignment.

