8.3 Tertiary Efficacy Endpoints

Tertiary Efficacy endpoints include:

- **Change from baseline** to 8 weeks post Relivion®DP treatment initiation **in the Clinical Global Impression Severity scale (CGI-S) score**.
- **Clinical Global Impression Improvement (CGI-I) score** over time **to Visit 4**.
- **Change from baseline** to week-8 post Relivion®DP treatment initiation **in the total score of the Quick Inventory of Depressive Symptomatology (self-rated)** (QIDS-SR-16).
- **Change from baseline** to week-8 post Relivion®DP treatment initiation **in depressive symptoms** as measured by **HDRS-21** total score.
- **HDRS-17 Total score** to week-8 post Relivion®DP treatment initiation.
- **Proportion of subjects achieving clinically substantial improvement in HDRS-17** - defined as the percent of subjects with reduction in HDRS-17 score of at least 7¹ points at 8 weeks post Relivion®DP treatment initiation.
- **HDRS-17 Category Shift from Visit 2 to Visit 4** – defined as the category change from baseline to week-8 post Relivion®DP treatment initiation in HDRS-17; Categories definition: 5: Very severe 26-52, 4: Severe 20-25, 3: Moderate 14-19, 2: Mild 13-8 and 1: 0-7 Remission.
- **Change from baseline Q-LES-Q score at Visit 4** – measured as the difference between the baseline and visit 4 Q-LES-Q percentage of maximum total scores.

¹ Rush AJ et al. Clinically Significant Changes in the 17- and 6-Item Hamilton Rating Scales for Depression: A STAR*D Report. Neuropsychiatric Disease and Treatment 2021;17:2333–2345

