9. SIGNIFICANCE LEVELS AND HANDLING OF TYPE I ERROR

9.1 Type I error

The overall significance level for this study is 5% using two-tailed tests, except for treatment by site interaction that will be tested at a significance level of 10% and the test for early efficacy at the interim look.

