11.5.2 Subset Analyses

The primary endpoint will be presented descriptively for the following subsets in addition they will be entered as additional covariates in the primary efficacy endpoint ANCOVA model to evaluate their effect on the change from baseline HDRS-17 score:

- Age Group (by median age)
- Sex (at birth)
- Baseline HDRS-17 severity (≥ 26 , 20-25, 17-19)
- Baseline Resistance, ATRF 1 vs. 2-4
- Concomitant anti-anxiety medication use, Yes/No
- Concomitant insomnia (includes anti-anxiety medications used to treat insomnia at bedtime) medication use, Yes/No
- Concomitant anticonvulsant medication use, Yes/No
- Comorbidities migraine and pain disorders, Yes/No
- Past history of ECT, TMS or VNS treatment, Yes/No
- Subjects on subtherapeutic dose of antidepressant, Yes/No
- Blinding assessment - The effect of potential unblinding will be evaluated as a sensitivity analysis, where an additional binary variable identifying subjects correctly guessed their treatment assignment versus those who did not will be added to the ANCOVA model as a covariate.

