11.5.5 Tertiary Endpoints Analyses

- Mean Change in the CGI-S score - at 8 weeks post treatment initiation– will be compared between the groups using a similar model as the primary endpoint.
- Mean CGI-I scores at 8 weeks post treatment initiation will be compared between the groups using a similar model as the primary endpoint but with the value at each visit modeled instead of the change.
- Mean change from baseline in total score of the Quick Inventory of Depressive Symptomatology self-rated (QIDS-SR-16) score at 8 weeks post treatment initiation– will be compared between the groups using a similar model as the primary endpoint.
- Mean change in depressive symptoms, measured by HDRS-21 total score, from baseline to week 8 post Relivion®DP treatment initiation will be compared between the groups using a similar model as the primary endpoint.
- Proportion of subjects with a clinically substantial reduction in HDRS-17 score defined as the percent of subjects with reduction in HDRS-17 score of at least 7 points at 8 weeks post Relivion®DP treatment initiation - will be summarized by a count and percentage and compared between the groups with a chi-squared test and a Fisher's exact test. The odds ratio with 95% Wald confidence interval will be presented as well. As an additional measure of effect size the NNT will be presented.
- HDRS-17 total score at visit 4 (week-8 post Relivion®DP treatment initiation) will be compared between the groups using a similar model as the primary endpoint using the HDRS-17 score at each visit instead of the change.
- HDRS-17 Category Shift from Visit 2 to Visit 4 – defined as the category change from baseline to week-8 post Relivion®DP treatment initiation in HDRS-17; Categories definition: 5: Very severe 26-52, 4: Severe 20-25, 3: Moderate 14-19, 2: Mild 13-8 and 1: 0-7 Remission, will be summarized by a count and

percentage and compared between the groups with a Cochran-Armitage trend test.

- Mean change in Q-LES-Q score at visit 4 – measured as the difference between the baseline and visit 4 Q-LES-Q percentage of maximum total scores, will be compared between the groups using analysis of variance (ANOVA).

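### The HDRS-17 category shift is compared without conditioning on baseline severity, so chance baseline imbalance carries into the result and some power is given up; the test is valid and the impact is low.

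*SAP*

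**What the plan says.** SAP 11.5.5 describes the endpoint as "defined as the category change from baseline to week-8 post Relivion®DP treatment initiation in HDRS-17". SAP 8.3 gives the bands: "Categories definition: 5: Very severe 26-52, 4: Severe 20-25, 3: Moderate 14-19, 2: Mild 13-8 and 1: 0-7 Remission". The arms are to be summarized by a count and "percentage and compared between the groups with a Cochran-Armitage trend test". No stratification factor or covariate is named for this test.

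Four other places bear on it:

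- SAP 11.5.2 plans a subset display by "Baseline HDRS-17 severity (≥ 26 , 20-25, 17-19", so subjects are expected in baseline categories 3, 4 and 5.
- SAP 6 allocates 1:1 by a "randomization scheme using the permuted block method stratified by center". Baseline severity is not a stratum.
- SAP 11.5.1 puts baseline HDRS-17 in the primary model as a continuous covariate. SAP 11.4 argues that chance imbalance in baseline values of the outcome can bias crude estimates and cost precision and power, and it recommends adjustment by ANCOVA.
- SAP 11.5.4 offers covariate-adjusted logistic regression for response and remission if prognostic factors are identified. Nothing similar is offered for the category shift.

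**The concern.** The shift a subject can show depends on where that subject starts, and the planned test pools raw shifts across starting points. Two things follow. Variation due only to starting severity stays in the error term. And if one arm happens to be more severe at baseline, part of that difference appears as a difference in shift.

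The cut-points add to this inside a category. A subject at 20 leaves category 4 by losing one point; a subject at 25 must lose six. The baseline score therefore carries information that the baseline category does not.

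At stake are the precision and the conditional fairness of one tertiary p-value. The primary result is not affected.

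**Working it through.** **1. Bounds on the shift.** Shift = Visit 4 category minus baseline category. With categories 1 to 5 and baseline category c, it lies between 1 - c and 5 - c:

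| Baseline category | Possible shift |
|---|---|
| 3 | -2 to +2 |
| 4 | -3 to +1 |
| 5 | -4 to 0 |

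**2. The plan's own sample size.** No power is stated for the category shift, so the primary calculation is the anchor. Protocol 12.4: "We use conservative estimates of a 3.3-point difference with a standard deviation of 6 points", and "a sample size of 53 subjects per group (total 106) would provide 80% power at a 5% level of significance (two-sided".

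n per arm = 2 × (1.960 + 0.842)² × 6² / 3.3² = 2 × 7.85 × 36 / 10.89 = 51.9, so 52 by the normal approximation. The noncentral t gives 80.1% power at 53 per arm. The plan's figure is reproduced.

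**3. Simulation inputs.** From the documents: 53 per arm, 3.3-point effect, SD of change 6, sham change of -5.4 (Protocol 12.4, a six-week figure used here for week 8), the SAP's five bands, and two-sided 5% ("The overall significance level for this study is 5% using two-tailed tests", SAP 9.1).

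Assumed, because the documents do not give them: baseline HDRS-17 normal with mean 20, 22 or 23, truncated at 17 (SD 2.5 to 3.6 after truncation), and baseline-to-week-8 correlation r of 0.2 to 0.6. With the SD of change held at 6, the week-8 SD solves SD₈² + SD₀² - 2·r·SD₈·SD₀ = 36, and the slope on baseline is r·SD₈/SD₀. For SD₀ = 3.12 and r = 0.3, SD₈ = 6.15 and the slope is 0.3 × 6.15 / 3.12 = 0.59.

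**4. Does the shift depend on the start?** At r = 0.3 and baseline mean 22, the sham mean shift is -0.32, -0.92 and -1.45 from categories 3, 4 and 5. It does.

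**5. Type I error.** Over all randomizations the planned test rejects in about 5% of null trials (4.9-5.2%).

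Now condition on the active arm being about 0.16 to 0.19 category more severe at baseline, roughly 1.5 SD of the chance difference. Null rejection in favor of active, against a nominal 2.5%, is:

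| r | Planned test |
|---|---|
| 0.2 | 5.5-7.5% |
| 0.3 | 5.0-5.9% |
| 0.4 | 4.1-5.1% |
| 0.5 | 3.1-4.7% |
| 0.6 | 2.2-2.8% |

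A Cochran-Mantel-Haenszel (CMH) mean-score test stratified by baseline category gives 1.8-3.1% for r = 0.2 to 0.4. Over that range the bias in mean shift is about -0.05 to -0.13 category, against a treatment effect of about -0.5. At r = 0.6 it is close to zero.

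**6. Power at 3.3 points.** Two simulation sets, each with its own run of the planned test. Set A has 40,000 trials per setting. Set B has 8,000 and uses a linear model of Visit 4 category on arm and baseline score.

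| r | Planned (A) | Stratified CMH (A) | Planned (B) | Score-adjusted (B) |
|---|---|---|---|---|
| 0.2 | 72-74% | 77-82% | 71-73% | 79-82% |
| 0.3 | 72-74% | 74-79% | 72-73% | 77-79% |
| 0.4 | 72-73% | 73-75% | 72% | 76% |
| 0.5 | 72% | 72% | 71-73% | 75-76% |
| 0.6 | 72-73% | 71% | 71-72% | 75-77% |

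The score-adjusted model gains about 3 to 9 points throughout, with null rejection of 4.6-5.3%. The gain from stratifying by category vanishes at r = 0.5 and turns slightly negative at 0.6.

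**7. The proportional-odds model itself.** Fitted to Visit 4 category with baseline score, for assumed slopes of 0.5 to 1.0 and 800 trials per setting: 74-79%, against 69-74% for the planned test, a gain of about 4 to 9 points. The Monte Carlo standard error of one such power is √(0.75 × 0.25 / 800) = 1.5 points.

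**The case against.** The strongest counter-argument is that this is a preference about a test that is already valid, in a place where little depends on it. Much of that stands.

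- **The gate.** SAP 9.2 reaches the tertiary endpoints only after the primary and secondary endpoints succeed. A simulation requiring primary ANCOVA, response and remission each at p < 0.05 (MADRS not simulated, baseline truncated at 16, slopes 0.5 to 1.0) opened the gate in 25-38% of trials. Among those, the planned test had 94-97% power against 96-99% for adjusted alternatives. The gate opened, the planned test missed and an adjusted test succeeded in only 0.3-1.8% of trials. The step-up adjustment was not modelled.
- **Other evidence.** Baseline-adjusted analyses of HDRS-17 are already planned, for the primary change and for the tertiary Visit 4 total score. Baseline comparisons would show an imbalance.
- **Consistency.** Response, remission and the 7-point reduction also have unadjusted main tests.
- **Endpoint.** Modelling the Visit 4 category changes what the inference is about.

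Four stronger readings might be inferred, and none is supported. The first is that the test is invalid; overall type I error is nominal, and the distortion is conditional on a chance imbalance. The second is that baseline is ignored altogether; the shift subtracts the baseline category, so what remains is mostly over-correction, and the category bounds the shift without determining it. The third is that any baseline adjustment would gain power; stratifying by category may gain nothing. The fourth is that this p-value certainly enters the tertiary step-up; SAP 9.2 counts seven tertiary endpoints, SAP 8.3 and 11.5.5 list eight, and the SAP does not say which is left out.

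What survives is that the SAP's own reasoning in 11.4 favors adjustment, the covariate is already collected, and the score-adjusted model gained power in every setting tried.

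**Conclusion.** The point holds as an optional refinement. The planned comparison is valid under randomization but does not condition on baseline severity. It therefore carries chance imbalance into the result, in the direction that flatters the more severe arm when baseline and week-8 scores are only modestly correlated. It has about 69-74% power where a proportional-odds model with baseline score has about 74-79%.

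Those figures rest on assumed baseline distributions and slopes, on complete data for 53 per arm, and on ignoring the hierarchical gate. Once the gate is taken into account the practical difference is small. No conclusion about the primary or secondary endpoints is touched.

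**What to change.** In SAP 11.5.5, replace the Cochran-Armitage comparison by a proportional-odds model of the Visit 4 HDRS-17 category, with treatment arm and baseline HDRS-17 total score as covariates. Keep the Visit 2 to Visit 4 shift table by arm as the descriptive display. Do not rely on the CMH test stratified by baseline category: its gain is small or nil when baseline and week-8 scores are well correlated.

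The cost is one SAP sentence and a few lines of code, with no new data. The downside is that the inferential comparison becomes the Visit 4 category adjusted for baseline instead of the raw shift, and the text should say so. The change should be made before the treatment code is opened; after that, the model belongs in the report as a labelled sensitivity analysis.

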### **9.1.2. Visit 2 – Baseline (Day -4 - 0) Eligibility evaluation, Randomization and device training.**

Written below are the assessments to be completed at Visit 2 (either on site or remotely):

- Eligibility assessment.
- PRO training for subjects self-reported questionnaire (QIDS-SR-16 and Q-LES-Q) (hard copy and/or electronic)
- Depression symptoms questionnaires:
  - By site qualified rater: HDRS21 (HDRS17- removing 4 last questions from the HDRS21), MDRS, CGI-S & CGI-I
  - By subject: QIDS-SR-16, Q-LES-Q. Subject self-reported questionnaire may be filled in electronically (ePRO) or by hard copy
- Document change in antidepressant medication, if any.
- Documented significant change in health status, if any.
- Suicidal intent assessment by the investigator team (C-SSRS).
- A review the study requirements with the subject to help ensure compliance.
- Randomization to Active Treatment or Sham Control.
- Subject will be provided with the device and the cellular app installed either on their personal iPhone or on a dedicated study iPhone, as applicable. Device and cellular iPhone, if required, may be provided to the subject at the site (in the case of an on-site visit) or by delivery (in the case of a remote visit)
- Device training will be performed by the study central trainer and may be performed during an on-site visit or in a remote fashion.

 Neurolief Brain Innovation	MOOD: CLINICAL INVESTIGATION PLAN	Doc No.: CL-CIP-201 Rev: REV.3 / 09June2021 Pg. 47 of 92
--	--	--

- Subject will read the User manual, the quick guide and will watch the instructional video and be trained on the device and recommended treatment regimen (detailed on the Relivion®DP Quick guide) by the study central trainer (on-site or remote).
- Device size will be adjusted to subject head circumferences.
- Subject will self-practice the device along with the mobile application to become familiar with its use and with the stimulation sensation.
- Blinding Assessment questionnaire (by hard copy or electronically (ePRO)
- Adverse events occurring during the visit will be documented.

Study visit 2 may occur in between study day -4 to study day 0 to allow for a device shipment to subject home and a remote device training. In any case, the day of the device training would be considered as study day 0.

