11.4 Prognostic Factor Analysis

This section is intended to provide the architecture for this evaluation and does not jeopardize the sanctity of this study because this evaluation is being conducted independent of the randomized treatment assignment. Although

randomization creates asymptotic balance in important prognostic factors, including baseline values of the outcome variable in finite samples an imbalance in such factors may occur notwithstanding randomization, this represents the difference between the expectation of a random process and its realization. Depending crucially on the correlation between the baseline covariate and the outcome variable, this chance imbalance may not only create a potential bias in crude estimates of treatment effect in the outcome variable but may also affect the precision with which such an effect is measured and the statistical power of the analysis. Adjustment through the ANCOVA model is recommended to reduce risk of bias whilst also improving the precision of estimates and the power of the statistical test (Egbewale et al. BMC Medical Research Methodology 2014, 14:49). Specifically, if there was a significant difference in the HDRS-17 or in the secondary endpoints response and remission rates detected between the active and sham groups at 8 weeks post treatment initiation, but a retrospective analysis determined that the effect may have been influenced by one or more covariates not defined in the randomization scheme, the conclusion drawn from the unadjusted results could be challenged (Egbewale et al. BMC Medical Research Methodology 2014, 14:49).

The protocol and Statistical Analysis Plan (SAP) are clear regarding the tests for poolability (12.9.6 of the study protocol) and subset analyses (12.9.1 of the study protocol) that should be conducted. From Section 12.9.6 of the study protocol:

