- **Clinical Global Impression Improvement (CGI-I) score over time to Visit 6.** The CGI-I score (from visit 3) will be modeled with a repeated measures ANCOVA model. The score will be modeled as a function of visit (categorical). LSmean CGI-I scores will be estimated from the model per visit and for the difference between visits and will be presented with 95% confidence intervals as well as level of significance (testing the null hypothesis LSmean=0). The CGI-I score at visit 6 will be compared to the score at visit 4.

- **Change from baseline to week-16 (visit 6) post Relivion®DP treatment initiation in the total score of the Quick Inventory of Depressive Symptomatology (self-rated) (QIDS-SR-16).** The change from baseline QIDS-SR-16 score will be modeled with a repeated measures ANCOVA model. The change will be modeled as a function of visit (categorical) with baseline value entered as a covariate. LSmean QIDS-SR-16 changes from baseline will be estimated from the model per visit and for the difference between visits and will be presented with 95% confidence intervals as well as level of significance (testing the null hypothesis LSmean=0). The change at visit 6 will also be compared to the change at visit 4.
- **Change from baseline Q-LES-Q score at Visit 6** – measured as the difference between the baseline and visit 6 Q-LES-Q percentage of maximum total scores. The change from baseline Q-LES-Q score will be modeled with a repeated measures ANCOVA model. The change will be modeled as a function of visit (categorical) with baseline value entered as a covariate. LSmean Q-LES-Q changes from baseline will be estimated from the model per visit and for the difference between visits and will be presented with 95% confidence intervals as well as level of significance (testing the null hypothesis LSmean=0). The change at visit 6 will also be compared to the change at visit 4.

2. The following endpoints will be analyzed on all subjects that completed visit 6 grouped together regardless of prior double-blind treatment:

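### The double-blind Q-LES-Q comparison names no baseline covariate: it is valid, but generally less precise than the baseline-adjusted model used for the other continuous change endpoints

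*SAP*

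**What the plan says.** SAP 11.5.5 defines the Q-LES-Q outcome as the change "measured as the difference between the baseline and visit 4 Q-LES-Q percentage of maximum total scores" and states that it "will be compared between the groups using analysis of variance (ANOVA". Neither baseline Q-LES-Q nor center is named as a model term.

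Other parts of the plan bear on this line:

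- **Collection.** Protocol 9.1.2 lists the self-reported scales at baseline: "By subject: QIDS-SR-16, Q-LES-Q". Protocol 9.1.5 lists the same two at visit 4. Q-LES-Q is not collected at visit 3 (Protocol 9.1.4 and Table 1).
- **Other change endpoints.** MADRS (SAP 11.5.4) and CGI-S, QIDS-SR-16 and HDRS-21 (SAP 11.5.5) each "will be compared between the groups using a similar model as the primary endpoint". That model, in SAP 11.5.1, has the baseline score as a continuous covariate.
- **Open-label Q-LES-Q.** SAP 11.5.7 says: "The change from baseline Q-LES-Q score will be modeled with a repeated measures ANCOVA model". It continues: "The change will be modeled as a function of visit (categorical) with baseline value entered as a covariate".
- **The SAP's own reasoning.** SAP 11.4 says: "Adjustment through the ANCOVA model is recommended to reduce risk of bias whilst also improving the precision of estimates".

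**The concern.** Among the continuous between-group change endpoints, Q-LES-Q is the only one assigned a model with no baseline term. The baseline value has to be available anyway, because the change score is computed from it. The SAP gives no reason for the exception, which runs against its general argument for adjustment.

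What is at stake is efficiency on a quality-of-life result. SAP 9.2 extends the testing hierarchy to the tertiary endpoints, with a Benjamini–Hochberg adjustment, if the primary and secondary endpoints are significant. The p-value could then support a claim, and it could also move the adjusted p-values of the other endpoints in that family.

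**Working it through.** **The plan's own figure.** The only sample size calculation is for HDRS-17 (Protocol 12.4): "We use conservative estimates of a 3.3-point difference with a standard deviation of 6 points". It gives 53 per group, 80% power and two-sided 5%. With d = 3.3/6 = 0.55, the exact two-sample t-test has 80.1% power at 53 per arm and 79.3% at 52, so 53 reproduces. Allowing for dropout, 106/0.85 = 124.7, against the stated 124. The documents give no effect size, SD or correlation for Q-LES-Q, so everything below rests on assumed values.

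**Does other text supply the baseline term?** No.

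- Baseline Q-LES-Q is not in the prognostic factor list of SAP 11.4.
- Factors found there are carried into the primary model (SAP 11.5.1) and into the response and remission analyses (SAP 11.5.4). No text carries them into the Q-LES-Q comparison.
- The general methods in SAP 11.1 offer a t-test or Wilcoxon test for means.
- The protocol's exploratory analyses (12.9.3) do not mention Q-LES-Q.

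**Precision.** Let s0 and s1 be the baseline and visit 4 SDs, rho their correlation and k = s0/s1.

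- Per-subject variance of the change score: s0² + s1² − 2·rho·s0·s1
- Per-subject residual variance under ANCOVA: s1²·(1 − rho²)
- Difference: s0² − 2·rho·s0·s1 + rho²·s1² = (s0 − rho·s1)², which is never negative
- Ratio, change score to ANCOVA: 1 + (k − rho)²/(1 − rho²)

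Excess variance of the change-score comparison:

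| Assumed k | rho 0.3 | rho 0.5 | rho 0.7 |
|---|---|---|---|
| 1.0 | 0.49/0.91 = 54% | 0.25/0.75 = 33% | 0.09/0.51 = 18% |
| 0.8 | 0.25/0.91 = 27% | 0.09/0.75 = 12% | 0.01/0.51 = 2% |
| 0.7 | 0.16/0.91 = 18% | 0.04/0.75 = 5% | 0/0.51 = 0% |

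The loss vanishes when rho = k. If k exceeds 1, it is larger than in the first row.

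**Simulation (k = 1).** 20,000 trials were run with 53 per arm and a true effect of 0.55 SD of the change score, chosen only so that the ANOVA has about 80% power.

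| rho | Variance, ANCOVA/ANOVA | Power, ANOVA | Power, ANCOVA | Correlation of ANOVA estimate with baseline imbalance |
|---|---|---|---|---|
| 0.3 | 0.66 | 80.4% | 93.4% | −0.59 |
| 0.5 | 0.76 | 80.1% | 89.5% | −0.50 |
| 0.7 | 0.85 | 79.9% | 86.1% | −0.39 |

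At k = 1 the ratio formula inverts to (1 + rho)/2 = 0.65, 0.75 and 0.85, which agrees. The ANCOVA estimate had a correlation of about 0 with baseline imbalance in all three cases.

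**Chance imbalance.** The regression slope of visit 4 on baseline is rho/k. A one-unit baseline difference between arms therefore moves the expected change-score estimate by −(1 − rho/k). At k = 1 this is −0.7, −0.5 and −0.3 for the three values of rho. At k = 0.7 it is −(1 − 0.43) = −0.57, −(1 − 0.71) = −0.29, and 0.

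**The case against.** **The word ANOVA is used loosely in this SAP.** Section 11.5.1 calls its own ANCOVA a repeated measures ANOVA, and section 11.4 uses the term for models with continuous factors. So the label alone does not prove a model without covariates. That is fair, but the Q-LES-Q entry lists no covariate and does not refer to the primary model, as the neighbouring change endpoints do. No other text supplies the baseline term. At the least, the model terms need stating.

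**A simpler method has a reason.** Q-LES-Q has one post-baseline double-blind assessment, so a repeated-measures model is not needed. That explains why there is no visit term. It does not explain why baseline is absent: the last open-label analysis in SAP 11.5.7 models a single change by ANCOVA with a baseline covariate.

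**The open-label model is not a direct precedent.** It covers only the original active arm, across visits, so its covariate does nothing about between-arm imbalance. This stands. The comparison shows inconsistent handling of one scale and no more. The stronger comparison is with the other between-group change endpoints.

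**The loss may be small.** This also stands. Entry requires HDRS-21 of at least 20, which may narrow the baseline spread of related scales and push k below 1. At some combinations of k and rho there is no loss.

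**Stronger readings that a reader might infer.** One is that the ANOVA is biased, or that it leaves chance baseline imbalance in the estimate untouched. Neither follows. Under the 1:1 randomization the change-score comparison is unbiased on average and keeps its type I error. Because it subtracts baseline, what remains is an over-correction when rho is below k, through regression to the mean. Another is that the variance penalty is 18% to 54%. That holds only for equal baseline and visit 4 variances, which the documents do not establish.

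**Conclusion.** The point holds as a question of efficiency and consistency. It does not make the analysis invalid. The planned comparison is never more precise in large samples than the baseline-adjusted one, and it is less precise unless rho equals k. Over the assumed values of k from 0.7 to 1 and rho from 0.3 to 0.7, the excess variance runs from 0% to 54%. The direction follows from the algebra, but the size depends on two quantities that the documents do not give.

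The reach is limited to one tertiary endpoint, and no primary or secondary conclusion is affected. Formal testing happens only after the primary and secondary endpoints succeed. SAP 9.2 counts seven tertiary endpoints while SAP 8.3 lists eight, so it is also not certain that Q-LES-Q belongs to the tested family.

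**What to change.** Replace the Q-LES-Q entry in SAP 11.5.5 with an ANCOVA of visit 4 Q-LES-Q change on treatment group, with baseline Q-LES-Q as a continuous covariate and center handled as in the primary model. SAP 11.5.1 is itself inconsistent on center (a covariate in the text, a random effect in the mock code). Settle that once and use the same choice here.

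The cost is one SAP line and one degree of freedom for the baseline term. No new data are needed. SAP section 6 states that the treatment code had not been revealed when the SAP was finalized, so the change should be made before unblinding. If that is no longer possible, report the ANCOVA alongside the planned ANOVA as a justified deviation, as SAP 11.1 provides.
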